8.1.2.2. Clinical Global Impression Scale—Domain Improvement Scores

Clinical Global Impression of Improvement assessments are completed at Visit 9 (Week 6), End of Treatment (Week 13, Visit 16), and Follow-up (Visit 17). The clinician rates

how much the subject's illness has improved or worsened relative to the baseline visit (Visit 3) in each domain. The seven domain improvement scores are: expressive communication, receptive communication, gross motor function, fine motor function, social interaction, self-care, and cognition/learning. The individual domain CGI-I scores are rated on a 7-point scale, where 1='very much improved'; 2='much improved'; 3='minimally improved'; 4='no change'; 5='minimally worse'; 6='much worse'; 7='very much worse'. Scores of 1, 2, and 3 indicate improvement.

Within subject change is indicated by the score at each relevant follow-up visit (Week 6, Visit 9 and Week 13, EOT, Visit 16). If a domain score is missing, that subject will be excluded from analysis for that domain. Domain scores will be presented in forest plots, as described in Section 8.1.2.

Domain scores as reported on the CRF will be summarized at each post-baseline visit, in the same manner as the CGI-I Overall Score.

8.1.2.4. Caregiver Impression of Change Score

The Caregiver Impression of Change assessment will be completed at the end of treatment visit (Week 13, Visit 16).

The caregiver is asked to rate the change in his or her child's overall function and well-being since the Baseline visit, and the change in specific symptoms. This is rated on a 7-point Likert scale: 1-Very much improved, 2-Much improved, 3-Improved, 4-Unchanged, 5-Worse, 6-Much worse, 7-Very much worse. Scores of 1, 2 or 3 indicate improvement in overall function and symptoms.

For the rating of overall function, the caregiver also identifies the one symptom area or feature that has most influenced his or her rating of the child's overall function and provides a description of symptom changes and impact of the changes. The assessment of change should be made since the Baseline visit (Visit 3). The caregiver should assess the subject's current state at the visit taking into consideration observations at the visit and symptoms within the last week.

The symptom domains rated are: communication, social interaction, behavior, motor abilities, seizures, cognitive abilities and ability to learn, support needed to perform daily

tasks, gastrointestinal (GI) symptoms, and sensory sensitivity problems. Within subject change is indicated by the score at EOT. If a score is missing for a domain, that subject will be excluded from the corresponding domain summaries. For the total score, the LOCF method will be used for the missing score and the total score will be calculated.

Summary statistics on the Caregiver Impressions of Improvement overall and domain scores will be displayed at End of Treatment. The overall score will be presented in waterfall plots, histograms, and violin plots, and the domain scores will be presented in a forest plot, as described in Section 8.1.2.

8.1.2.5. Clinical Global Impression Scale—Severity (CGI-S)—Overall Severity Score

Clinical Global Impression of Severity assessments will be made at the Screening visit (Visit 1), Baseline (Visit 3), Visit 9 (Week 6), End of Treatment (Week 13, Visit 16), and Follow-up (Week 15, Visit 17). The overall severity score is scored on a 7-point scale, where 1='not at all impaired'; 2='borderline, slightly impaired'; 3='mildly impaired'; 4='moderately impaired'; 5='markedly impaired'; 6='severely impaired'; 7='among the most severely impaired'. Lower scores reflect less impairment. Within subject change is the difference between the score at EOT and the score at Baseline (Visit 3). If a score is missing, the subject will be excluded from the corresponding summaries.

The overall score and change from baseline at each post-baseline visit will be summarized using descriptive statistics. Within-subject changes will be analyzed using a Wilcoxon signed rank test. Test-retest reliability will be assessed for all scores collected during the Screening period (Visits 1, 2, and 3, pre-dosing) using Intraclass Correlation Coefficients (ICC). The overall score will be presented in waterfall plots, histograms, and violin plots, as described in Section 8.1.2.

8.1.2.6. Clinical Global Impression Scale—Severity (CGI-S)—Domain Scores

Clinical Global Impression of Severity assessments will be made at the Screening visit (Visit 1), Baseline (Visit 3), Visit 9 (Week 6), End of Treatment (Week 13, Visit 16), and Follow-up (Week 15, Visit 17). The seven domain severity scores are: expressive communication, receptive communication, gross motor function, fine motor function, social interaction, cognition/learning and self-care. Each domain score is scored on a 7-point scale, where 1='not at all impaired'; 2='borderline, slightly impaired'; 3='mildly impaired'; 4='moderately impaired'; 5='markedly impaired'; 6='severely impaired'; 7='among the most severely impaired'. Lower scores reflect less impairment. Within subject change is the difference between the total score at EOT and the score at Baseline (Visit 3). If a score is missing, the subject will be excluded from the corresponding summaries.

The CGI-S domain scores will be analyzed in the same manner as the CGI-S overall score.

8.1.2.7. MacArthur-Bates Communicative Development Inventory (MB-CDI) Scores

The MacArthur-Bates Communicative Development Inventory (MB-CDI) will be completed at Baseline (Visit 3) and End of Treatment (Week 13, Visit 16). This caregiver-completed instrument assesses language development in vocabulary comprehension and production, gestures, and grammar. Designed to assess early language development in infants and toddlers, it can also be used with older, developmentally delayed children to assess developmental progress in language development. Children are assessed on one of three modules based on chronological or developmental age: Words and Gestures (8 to 18 months or developmental equivalent), Words and Sentences (16 to 30 months or developmental equivalent) and the CDI-III, an extension of the MB-CDI used with children 30 to 37 months (or developmental equivalent). The appropriate module will be used for this study in line with the cognitive and language development of the individual subject.

In the Words and Gestures module, the number of phrases understood, the number of words understood, number of words produced, number of early gestures, number of later gestures, and number of gestures will be summarized. The number of "yes" answers in "First signs of understanding" and "Starting to Talk" will be summarized. In the Words and Sentences module, the number of words produced, number of word forms, number of word endings, and the number of times a more complex sentence is selected will be summarized. In the EDC, for "words produced" in the WS module, a duplicate empty field was available in the EDC. For the analysis, the data entered in field variable name MBCDI2_CDINUM is used for analysis. For the CDI-III module, the total number of words recognized in the Vocabulary Checklist, the number of responses where the more complex sentence was chosen in Sentences, and the number of "Yes" responses in Using Language will be summarized. All other MB-CDI results will be presented in listings.

Change from baseline for the scores from the module completed for the child will be analyzed using a Wilcoxon signed rank test. To summarize data across the modules, the data on vocabulary will be presented for all subjects in a summary table. This will include the relevant scores from which ever module was completed: WG (the number of words understood); WS (number of words produced), CDI-III (total number of words for vocabulary). The vocabulary score will be presented as waterfall plots, histograms, and violin plots as described in Section 8.1.2. Exemplars of new words may be listed for individual subjects who show increases in vocabulary.

8.1.2.8. Observer-Reported Communication Ability (ORCA) Score

The Observer-Reported Communication Ability (ORCA) measure will be completed at Baseline (Visit 3) and End of Treatment (Week 13, Visit 16). This caregiver-reported measure was developed to assess communicative abilities in verbal and low-verbal/non-verbal populations. The caregiver evaluates the individual's observed communication ability over the past 30 days. The ORCA measure will be scored using the R code provided by the developers of the measure. The macro will produce an ORCA t-score as long as at least one of the 20 concepts or items has a score. A concept score will be given only if all the items within the concept are answered. Higher scores reflect greater communication ability. The ORCA t-score range is 26.82 to 83.24.

A modified t-score will be also calculated. The SAS macro used to calculate the total score will be edited to give credit for both "always" and "sometimes" responses. This edited macro will be used to calculate the modified t-score.

The t-score and modified t-score will be summarized using descriptive statistics. Change from baseline will be analyzed using a Wilcoxon signed rank test. The t-score and modified t-score will be presented in waterfall plots, histograms, and violin plots, as described in Section 8.1.2.

8.1.2.9. Caregiver Top 3 Concerns Rating

The Caregiver Top 3 Concerns Rating assessment will be completed at all Screening and Baseline visits (Visits 1, 2, 3), as well as Week 6 (Visit 9), End of Treatment (Week 13, Visit 16), and Follow-up (Visit 17). The three concerns identified at Screening/Baseline are carried forward and rated at the follow-up visits. The severity of each concern is scored using a 10-point Likert scale of severity. Lower scores indicate lesser severity. The overall score will be calculated as a sum of the scores across all domains. The overall score will have a range of 0 to 30.

If the caregiver does not list the same 3 concerns on the Top 3 Concerns Follow-Up CRF that were recorded on the Top 3 Concerns CRF (completed at Visit 1), then their responses will be reviewed and may not be included in analysis. A review of all concerns will be done prior to database lock, and visits with incorrect concerns will be flagged as unusable for analysis.

The frequency of any symptom being chosen by concern number, along with all concerns combined will be summarized. Summary statistics for the change from baseline in the overall and the concern scores and by symptom domain will be displayed at all post-baseline visits. Test-retest reliability will be assessed for all scores collected during the Screening period (Visits 1, 2, and 3, pre-dosing) using Intraclass Correlation Coefficients

(ICC). The overall and concern scores will be presented in waterfall plots, histograms, and violin plots, and the domain scores at baseline will be presented in a forest plot, as described in Section 8.1.2.

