9.5.9.7 Caregiver Top 3 Concerns Rating

The Caregiver Top 3 Concerns Rating assessment is a syndrome-specific measure of 3 signs or symptoms of PMS identified by caregivers at Baseline as being priority concerns in which they would like to see improvement as a result of treatment. The assessment will be completed at all Screening and Baseline visits (Visits 1, 2, 3), as well as Week 6 (Visit 9), EOT (Week 13, Visit 16), and the Follow-up (Visit 17).

In this assessment, concerns are identified on an individual, per-subject basis. The clinician should review the assessment with the caregiver at the Screening visit, ideally as part of the overall medical and clinical history. Caregivers should be encouraged, in selecting the concerns, to identify distinct, observable symptoms rather than broad ones. And caregivers should be advised to consider symptoms that they feel are important and have an impact on their child's daily functioning and well-being.

Caregivers are asked to identify 3 concerns from among 10 clinically important symptom domains: Communication, Social interaction, Gross motor skills, Fine motor skills, Behavior, Gastrointestinal problems, Seizures, Sleep, Sensory Sensitivity, and Self-care skills. Each individual concern identified should be from a different symptom domain, but caregivers can select any domain, and choose any symptom of concern within that domain. The same three concerns identified at Screening/Baseline are carried forward and rated at the follow-up visits. The severity of each concern is scored by caregivers using a 10-point Likert scale of severity. In rating, the caregiver should give consideration to symptoms within the last two weeks.

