1.2. Study Design

This is a Phase 2, open-label study of the safety and tolerability of NNZ-2591 Oral Solution, 50mg/mL Investigational Medicinal Product (IMP) in male and female children and adolescents with Phelan McDermid Syndrome. Approximately 20 male and female subjects between the ages of 3 and 12 years will be enrolled and receive treatment of NNZ-2591 Oral Solution, 50mg/mL IMP for a total of 13 weeks. The target dose will be attained following 6 weeks of up-titration.

There will be a total of 17 study visits, comprising 5 in-clinic visits and 12 remote telemedicine/in-home nurse visits. The study will commence with an approximately 4-6 week Screening and Baseline period. During this Screening/Baseline period, subjects will be assessed for study eligibility and data will be collected to establish the subject's baseline characteristics and symptom severity using a variety of assessments. Two

in-clinic visits and one remote/in-home visit (Visits 1, 2, 3) comprise Screening and Baseline.

Once eligibility is confirmed, subjects will be dosed with the starting dose of 4 mg/kg and then be up-titrated to the target dose 12 mg/kg BID. Subjects will receive IMP for a total of 13 weeks. During the treatment period, there are three in-clinic visits: Week 2 (Visit 5), Week 6 (Visit 6) and Week 13 (Visit 16). There is a combined telemedicine/in-home visit by the site Investigator and an in-home visit by a visiting nurse for safety at Week 1 (Visit 4), Week 4 (Visit 7), Week 8 (Visit 11) and Week 10 (Visit 13). These combination telemedicine/in-home visits will be conducted simultaneously whenever possible, or they will be conducted on the same day with the telemedicine visit occurring first if possible. In-home visits with a visiting nurse will be done at Weeks 3 (Visit 6), 5 (Visit 8), 7 (Visit 10), 9 (Visit 12), 11 (Visit 14), and 12 (Visit 15).

All subjects will also have a combined telemedicine/in-home follow-up visit with the Investigator via telemedicine and an in-person home visit by a visiting nurse approximately 2 weeks after the end of treatment (Week 15, Visit 17).

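### SAP 8.1.2.9 excludes Top 3 Concerns data by whole visit, so one replaced concern can discard two matched ratings, and neither the criterion nor masking to ratings is stated

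*SAP*

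**What the plan says.** Protocol 9.5.9.7 has the caregiver choose three concerns, each from a different symptom domain, and rate each on a 10-point severity scale. "The same three concerns identified at Screening/Baseline are carried forward and rated at the follow-up visits". It has no rule for a follow-up form on which the concerns differ.

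SAP 8.1.2.9 supplies one in three steps:

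- **Trigger:** "If the caregiver does not list the same 3 concerns on the Top 3 Concerns Follow-Up CRF" that were recorded at Visit 1, "then their responses will be reviewed and may not be included in analysis".
- **Timing:** "A review of all concerns will be done prior to database lock".
- **Consequence:** "visits with incorrect concerns will be flagged as unusable for analysis".

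The same section sets out what is analysed. For the total, "The overall score will be calculated as a sum of the scores across all domains", with a range of 0 to 30. Summaries are planned for the "change from baseline in the overall and the concern scores and by symptom domain" at every post-baseline visit.

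The section does not say what makes a concern incorrect, who reviews, whether that person sees the ratings, or whether exclusions will be counted. SAP 1.2 describes the trial: "This is a Phase 2, open-label study of the safety and tolerability".

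**The concern.** A rating of a different symptom has no baseline to be compared with, so leaving it out is reasonable. The difficulty lies in how the exclusion is done.

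- **Unit.** Each concern is a separate item from a separate domain. Replacing one does not invalidate the other two, yet the flag falls on the visit.
- **Criterion.** One sentence makes exclusion optional after review and the next makes it mandatory for visits judged incorrect. Without a definition, a reworded concern and a replaced concern could be treated alike or differently from child to child.
- **Masking.** The reviewer may be able to see the ratings. If so, the choice of which visits to keep could follow the scores, whether or not anyone intends it.

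At stake are usable ratings from a sample of about 20 children, and the reader's confidence that the exclusions did not depend on the result.

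**Working it through.** **1. Is there a plan figure to reproduce?** No. The sample-size section (SAP 4.1) concerns CGI-I only. No mismatch rate, expected loss or target effect is given for the Top 3 Concerns.

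**2. How the SAP treats other multi-part scales.** For CGI-I domains (SAP 8.1.2.2), a missing domain score removes the subject from that domain only. For ABC-2 and Vineland (SAP 8.1.2.10 and 8.1.2.14), a missing score removes the subject from the corresponding summaries. Section 8.1.2.9 departs from this component-level pattern and gives no reason.

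**3. What the unit costs.** Let q be the chance that any one concern is mismatched at a visit. The documents do not give q; I assume 2% to 20%, independent across the three concerns, and that every mismatch leads to a flag.

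- Share of visits flagged: 1 − (1 − q)³.
- Share of correctly matched ratings discarded (at least one of the other two concerns is mismatched): 1 − (1 − q)².

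| q (assumed) | Visits flagged | Visits left of 20 | Matched ratings discarded |
|---|---|---|---|
| 2% | 1 − 0.98³ = 5.9% | 18.8 | 1 − 0.98² = 4.0% |
| 5% | 1 − 0.95³ = 14.3% | 17.1 | 1 − 0.95² = 9.75% |
| 10% | 1 − 0.90³ = 27.1% | 14.6 | 1 − 0.90² = 19.0% |
| 20% | 1 − 0.80³ = 48.8% | 10.2 | 1 − 0.80² = 36.0% |

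Example at q = 5%: 20 children give 20 × 3 = 60 ratings, of which 60 × 0.05 = 3 are mismatched and 57 matched. Visit-level flagging also discards 57 × 0.0975 = 5.6 matched ratings. Concern-level exclusion discards none of them in the concern and domain summaries.

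The overall sum needs all three concerns. It is unavailable for 1 − (1 − q)³ of visits under either unit.

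**4. What discretion could do at worst.** Take 20 children with no true change and normally distributed changes. Flag k visits unrelated to the change, and drop a flagged visit only when its change is unfavourable. The number of flagged visits kept, B, is binomial(k, ½), and each kept one has mean −√(2/π) = −0.798 SD. The expected mean change is −0.798 × E[B/(20 − k + B)]. For k = 2 this is −0.798 × (0.5 × 1/19 + 0.25 × 2/20) = −0.041 SD. Rejection rates come from simulating the exact signed-rank test, two-sided at 0.05, with 400,000 runs.

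| Flagged of 20 | Mean shift (SD) | Rejection |
|---|---|---|
| 2 | −0.04 | 5.1% |
| 4 | −0.09 | 6.2% |
| 6 | −0.14 | 8.4% |
| 8 | −0.19 | 12.1% |

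A shorter run of 6,000 gave 5.6%, 5.8%, 8.0% and 12.8%, which agrees within simulation error. With nothing excluded the exact size is 4.8%. Dropping every flagged visit whatever its score leaves no shift and a size of 4.3% to 4.9%. That last result holds because flagging was made unrelated to change.

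**5. Carry-forward.** SAP 4.2.3 fills missing items by last observation when three or fewer are missing in a completed assessment. This scale has only three items, so that limit never bites. An excluded rating treated as a missing item could be replaced by an earlier one. Section 8.1.2.9 does not say whether that applies.

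**The case against.** The strongest case against the point is that this is a clarification request. The concerns are meant to be fixed, caregivers are trained before rating, and the Investigator reviews caregiver assessments at the clinic and follow-up visits. A mismatch should therefore be rare and may be a simple form error. The check is made before database lock, results for each efficacy variable are listed by subject (SAP 8.1.2), and there is no primary efficacy variable.

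Most of this stands and limits the weight of the point. It does not settle the unit of exclusion: discarding matched ratings is a choice with a better alternative already used elsewhere in the SAP. Reviewing before lock fixes the timing but does not withhold scores in an open-label trial. A listing lets a reader see what was dropped but does not govern the decision.

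Two stronger readings should be set aside. A reader might infer that the reviewer sees the ratings; the SAP is silent, so the supportable statement is that masking is not specified. A reader might also infer that any changed concern removes the visit automatically. A mismatch triggers a review, after which the responses may or may not be kept, and a reworded but equivalent concern could survive.

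**Conclusion.** The point holds as a cheap improvement. Whole-visit flagging can lose up to two matched ratings for one replaced concern, the two sentences differ in force, the criterion is undefined, and score-dependent exclusion is not prevented.

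Its actual size is unknown. The 4% to 36% loss of matched ratings rests on an assumed, independent mismatch rate and the strictest reading of the rule. The shift of 0.04 to 0.19 SD is a worst case in which every unfavourable flagged visit is dropped. Nothing in the documents shows that either will happen. The effect is confined to one of many secondary endpoints, with nominal significance levels (SAP 7.5).

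Two further inferences are not supported. One is that mismatches track outcome, for instance because a concern resolved: this is possible, but no document gives evidence for it, and a text-only review would not remove such a link. The other is that changing the unit would rescue the overall score: a sum of three ratings cannot be formed validly when one belongs to another symptom.

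**What to change.** Replace the mismatch paragraph in SAP 8.1.2.9 with one rule:

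- Before database lock, a named role compares each follow-up concern with the Visit 1 concern from the concern text only, with all ratings withheld. The answer is match or no match: same symptom, rewording allowed.
- Only a mismatched concern is excluded from the concern and domain summaries; matched ratings from that visit are kept.
- The overall sum for that visit is set to missing, and the item carry-forward in 4.2.3 does not fill the excluded rating.
- The number of exclusions and the reason for each are reported by visit.

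A sensitivity analysis with all visits included is not needed. If one is wanted, label it as mixing ratings of different symptoms, because it is not change from baseline in the chosen concerns.

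The cost is a listing of concern text without scores and one SAP paragraph. No new data are collected.

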8.1.2.10. Aberrant Behavior Checklist-2 (ABC-2)

The Aberrant Behavior Checklist-2 (ABC-2) will be completed at all Screening and Baseline visits (Visits 1, 2, 3), as well as Week 6 (Visit 9), End of Treatment (Week 13, Visit 16), and Follow-up (Visit 17). Each item is scored on a 4-point scale, where 0 = Not at all a problem; 1 = The behavior is a problem but slight in degree; 2 = The problem is moderately serious; 3 = The problem is severe in degree. The items are grouped into 5 subscales: Irritability (Subscale I, score ranges from 0 - 45), Social Withdrawal (Subscale II, score ranges from 0 - 48), Stereotypic Behavior (Subscale III, score ranges from 0 - 21), Hyperactivity/Noncompliance (Subscale IV, score ranges from 0 - 48), and Inappropriate Speech (Subscale V, score ranges from 0 - 12). The total score has a range from 0 - 174. Lower scores indicate fewer behavior issues. The subscale scores were calculated via a scoring algorithm in the EDC. These calculated scores will be used for the analysis. Missing items will be imputed as defined in section 4.2.3. Subscale or total scores may be calculated from answered and imputed items. If a total or subscale score is missing, then that subject will be excluded from the corresponding summaries.

Within subject change is the difference between the score at each measured timepoint and the score at Baseline (Visit 3). Summary statistics for the change from baseline in total and each subscale ABC-2 score will be displayed at all post-baseline visits. Change from baseline in the total and subscale scores will be analyzed using the Wilcoxon signed rank test. Test-retest reliability will be assessed for all scores collected during the Screening period (visits 1, 2, and 3, pre-dosing) using Intracass Correlation Coefficients (ICC). The total score will be presented in waterfall plots, histograms, and violin plots, and the subscale scores will be presented in a forest plot, as described in Section 8.1.2.

